2.2 Secondary Objectives

Secondary measures of therapy effectiveness will include:

1. To evaluate the effect of conventional pulse widths <500 μ sec and pulse widths >1000 μ sec on clinical outcomes during temporary trial as measured by the percent reduction in targeted pain compared to baseline using the NRS at the end of the trial period.
2. At end of each arm, subjects will be asked to complete a diagram that shows distribution of paresthesia.
3. At the end of the trial period, subjects will be asked to select their favorite program.
4. At the end of the trial period, subjects will be asked to rate the quality of the pain relief achieved during the trial (from either arm) using the following scale; *Excellent, Very Good, Good, Fair or Poor*
5. At the end of the trial period, subjects will be asked to rate their overall satisfaction with the pain relief achieved during the trial (from either arm) using the following scale; *Very Satisfied, Satisfied, Neither Satisfied nor Unsatisfied, Unsatisfied or Very Unsatisfied*
6. Number of patients who achieved $\geq 50\%$ pain relief during the trial (from either arm)
7. Rate of device-related and/or procedure-related AEs from SCS implant through study completion or study exit.

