5.2 SECONDARY ENDPOINTS

Endpoints for secondary measures of therapy effectiveness:

- To evaluate the effect of conventional pulse widths and pulse widths $>1000\mu\text{sec}$ clinical outcomes during temporary trial as measured by the percent reduction in targeted pain compared to baseline using the NRS at the end of the trial period.
- Comparison of paresthesia overlap of pain between each arm as evaluated by the reviewer to determine which arm had superior pain overlap (coverage)
- Patient *preference* for pulse widths $>1000\mu\text{sec}$ or $<500\mu\text{S}$
- Patient *satisfaction* for pulse widths $>1000\mu\text{sec}$ or $<500\mu\text{S}$
- Number of patients who achieved $\geq 50\%$ pain relief during the trial (from either arm)
- Rate of device-related and/or procedure-related AEs from Trial Lead implant through study completion.

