9.1.6 STUDY EXIT

A Study Exit CRF must be completed for any subject who signed an informed consent form, as they are considered enrolled in the study. Data to be collected at this visit includes:

- Record paresthesia and pain map for current arm
- Record pain rating for current arm
- Record program preference

- Record satisfaction and pain relief from each program
- Study exit date and reason for study exit

Additional data that will be collected as they occur include:

- Device or procedure related AEs
- Technical Observations/Device Deficiencies
- Surgical Interventions

The following scenarios may lead to study exit and will require completion of a Study Exit CRF.

- Inclusion/exclusion criteria not met
- Subject ineligibility for implant, in the opinion of the study physician
- SCS lead removal without re-implantation
- Implant attempted, however no SCS was implanted
- Voluntary withdrawal by subject
- Investigator chooses to withdraw a subject
- Failure to maintain adequate study compliance
- Subject Death

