11.2 Safety Analysis

All patients who received treatment will be included in the safety analysis. The proportion of patients with complications will be compared by Fisher's Exact test. The two treatment groups will be compared using t-test for continuous variables and chi square test for category variables. All adverse events will be listed and the frequencies, severity, and relationship to the treatment procedure will be tabulated and compared by treatment groups.

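### The one stated test that could apply to the five-level relief and satisfaction ratings is chi-square, which would discard both their order and the crossover pairing

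*Combined protocol and SAP*

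**What the plan says.** Section 11 has two subsections, one on the study population and one headed Safety Analysis. There is no effectiveness analysis section. Section 11.2 names three tests:

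- For complications: "The proportion of patients with complications will be compared by Fisher's Exact test".
- For everything else: "The two treatment groups will be compared using t-test for continuous variables and chi square test for category variables".

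Section 2.2 defines two ordered five-level scales. Relief quality is rated "Excellent, Very Good, Good, Fair or Poor". Satisfaction is rated "Very Satisfied, Satisfied, Neither Satisfied nor Unsatisfied, Unsatisfied or Very Unsatisfied".

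The protocol is not consistent about what is rated:

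- Section 2.2 (and the synopsis) asks subjects to "rate the quality of the pain relief achieved during the trial (from either arm) using the following scale" and to "rate their overall satisfaction with the pain relief achieved during the trial (from either arm) using the following scale". That is one answer per scale for the whole trial.
- Section 9.1.6 says "Record satisfaction and pain relief from each program". The synopsis exit list and the assessment tables in the synopsis and sections 4.1 and 9.1.1 say the same in substance. Section 5.2 lists satisfaction by pulse width as a secondary endpoint. That implies two answers per subject, one for each program.

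**The concern.** A Pearson chi-square on a table of 2 programs by 5 levels gives the same p-value if the level labels are shuffled. A consistent move toward better ratings is spread over 4 degrees of freedom and treated like any other pattern. The study asks whether longer pulse width gives better outcomes, so direction is the point of interest.

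The test also assumes that the two rows come from different people. In a crossover with per-program ratings, each subject contributes to both rows, and the within-subject information is lost.

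At stake is a real difference in satisfaction or relief between pulse widths going undetected on secondary endpoints. The primary endpoint is not affected.

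**Working it through.** The plan states no power or sample-size calculation, so it has no figure to reproduce.

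**Inputs from the protocol.** Five levels per scale (section 2.2), so the chi-square has (2 − 1) × (5 − 1) = 4 df. Crossover, at least 50 subjects (section 4.0), at most 100 (section 8.3).

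**Assumed, because the protocol is silent.** Two-sided 5%; a shift in one direction; the category mix; within-subject correlation 0 to 0.7; no period or carryover effect. Section 8.0 gives up to 10 subjects undergoing the trial; that size was not examined.

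**Step 1. Order alone, analytically.** Find the noncentrality λ that gives a 1-df ordered test a chosen power, then evaluate a 4-df chi-square at the same λ. For 80% power, λ = (1.960 + 0.842)² = 7.85, and P(noncentral χ² with 4 df exceeds 9.49) = 59.5%. The loss is 80 − 59.5 = 20.5 points.

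| Ordered test, 1 df | λ | Chi-square, 4 df | Loss (points) |
|---|---|---|---|
| 30% | 2.06 | 17.6% | 12.4 |
| 50% | 3.84 | 30.8% | 19.2 |
| 60% | 4.90 | 38.9% | 21.1 |
| 70% | 6.17 | 48.2% | 21.8 |
| 80% | 7.85 | 59.5% | 20.5 |
| 90% | 10.51 | 74.0% | 16.0 |
| 95% | 12.99 | 83.7% | 11.3 |

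**Step 2. Order alone, by simulation with uncorrelated ratings.** Proportional-odds shift; uniform, bell-shaped and skewed mixes; 1,000 runs per setting. Loss is Mann-Whitney power minus chi-square power, in points.

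| Odds ratio | 50 per program | 100 per program |
|---|---|---|
| 1.5 | 7 to 10 | 14 to 16 |
| 2 | 17 to 20 | 19 to 23 |
| 2.5 | 21 to 24 | 11 to 12 |
| 3 | 18 to 21 | 4 to 6 |
| 4 | about 10 | under 1 |

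**Step 3. Order and pairing together.** Two answers per subject, bell-shaped mix, odds ratio 2. The order column is Mann-Whitney minus chi-square. The pairing column is signed-rank minus Mann-Whitney.

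| N | Correlation | Chi-square | Mann-Whitney | Signed-rank | Order | Pairing |
|---|---|---|---|---|---|---|
| 50 | 0 | 29.9% | 49.9% | 47.2% | 20.0 | −2.7 |
| 50 | 0.3 | 23.3% | 46.2% | 56.2% | 22.9 | 10.0 |
| 50 | 0.5 | 20.7% | 48.0% | 70.1% | 27.3 | 22.1 |
| 50 | 0.7 | 13.9% | 44.4% | 86.9% | 30.5 | 42.5 |
| 100 | 0.5 | 55.0% | 83.8% | 95.8% | 28.8 | 12.0 |

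For correlations up to 0.5, the largest order-only loss in these runs is 74.6 − 42.4 = 32.2 points (N = 50, odds ratio 2.5, correlation 0.5). At correlation 0.7 it reaches 80.0 − 39.9 = 40.1. That figure compares two unpaired tests that reject only 2.0% and 0.0% of the time under no effect, so it is not used for the headline range.

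With no effect and correlation 0.5, chi-square rejects 2.2% of the time at N = 50 and 3.0% at N = 100. Signed-rank rejects 5.6% and 5.2%.

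**Step 4. A second model.** Latent-normal ratings, N = 50, levels at 15/20/30/23/12%. At correlation 0 and shifts of 0.4 and 0.5 SD, chi-square has 27% and 40% power against 46% and 63% for the rank test. At correlation 0.3, chi-square has 23% and 43% against 57% and 77% for signed-rank. The gap at 0.4 SD is 57 − 23 = 34 points. Separate runs of the 0.4 SD, correlation 0.3 case gave 23 to 25% against 57 to 59%.

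**The case against.** The strongest reply is that there may be nothing to compare. Section 2.2 attaches the five-level scales to one overall rating. None of the per-program lines says that the five-level scale is used for each program, and section 5.2 does not list relief quality by pulse width. If section 2.2 governs, no paired ratings exist and no power is lost. This stands as a condition on the point. It also leaves the section 5.2 endpoint on satisfaction by pulse width without data on this scale.

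Second, the chi-square sentence sits under Safety Analysis. A reader might infer that the plan assigns chi-square to the effectiveness ratings, but the protocol does not say so. If 11.2 covers safety only, these ratings have no stated test and the same paragraph is needed. Nor is chi-square the only categorical rule, since Fisher's test is named. The t-test would use the order of 1-5 scores, but the plan does not score the ratings, and as worded it too compares two groups rather than pairs.

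Third, a reader might take 20 points as a property of the plan. It is not: the loss is small for weak or very strong effects, and a difference that does not run in one direction can favour chi-square.

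Fourth, the point might be stretched to adverse-event severity. The section 5.2 safety endpoint is "Rate of device-related and/or procedure-related AEs from Trial Lead implant through study completion", a rate and not an ordered grade. Section 11.2 names no test in its sentence on severity, and nothing was calculated for it, so the point does not extend there.

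Finally, tabulated ratings would still show which program was rated better, and these are secondary endpoints. Both are fair, and they limit the weight of the point.

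**Conclusion.** The point holds conditionally: if the ratings are given per program and 11.2 is carried over to them, the only fitting test in the plan ignores both their order and the pairing.

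For 50 to 100 subjects, two-sided 5%, a one-directional shift and correlation up to 0.5, ignoring order alone costs from near 0 to roughly 30 points. It costs about 20 when the ordered test would have 50 to 80% power. Ignoring the pairing adds to this once the two answers are positively correlated, and adds nothing at zero correlation. All of these figures rest on assumptions that the protocol neither states nor contradicts.

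A reader might also expect false positives from ignoring the pairing. With positive correlation the calculations show the reverse: chi-square falls below its nominal 5%, so the harm is missed differences. This should be corrected, but it does not threaten the primary comparison.

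**What to change.** 1. Reconcile section 2.2 and the synopsis objectives with section 9.1.6, the synopsis exit list and the assessment tables. Confirm that each five-level scale is rated once per program. If only an overall rating is intended, describe it without a pulse-width comparison and revise the satisfaction endpoint in section 5.2 to match.
2. Add an effectiveness paragraph to section 11. Score the ratings 1 to 5 and compare programs within subject by a paired ordinal method that allows for period, at a stated significance level. One choice is a proportional-odds mixed model with program, period and subject. Another is a rank test on within-subject differences stratified by sequence. A plain signed-rank test, used above only to size the loss, ignores period. Period matters here because the tables place both ratings at study exit, when the second program is the more recent.
3. Keep chi-square or Fisher's test for unordered categories compared between independent groups.

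The cost is one paragraph and a little more analysis work. If the case report form now collects only an overall rating, each subject gives one extra answer per scale.

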- Compare the change from baseline of pain scores between the two study arms. Pain scores are obtained using the Numeric Rating Score (NRS) administered at baseline and after completion of each arm of the study.
- Paresthesia distribution: At end of each arm, subjects will be asked to complete a diagram that shows distribution of paresthesia.
- At the end of the trial period, subjects will be asked to select their favorite program.
- At the end of the trial period, subjects will be asked to rate the quality of the pain relief achieved during the trial (from either arm) using the following scale; *Excellent, Very Good, Good, Fair or Poor*.
- At the end of the trial period, subjects will be asked to rate their overall satisfaction with the pain relief achieved during the trial (from either arm) using the following scale: *Very Satisfied, Satisfied, Neither Satisfied nor Unsatisfied, Unsatisfied, or Very Unsatisfied*.

Secondary Safety Objectives Secondary measures of therapy safety will include:

- Rate of device-related and/or procedure-related AEs from the Trial procedure through study completion.

Study Procedures After the subject has consented to the study, he or she will be enrolled in the clinical study and undergo a baseline evaluation. The patient will then be randomly assigned to arm one (pulse width <500 μ sec) or arm two (pulse width >1000 μ sec) and undergo an Algovita® trial procedures. Following the trial procedure, the subject's EPG will be set to the appropriate pulse width, based on the arm assigned, and then programmed to achieve optimal pain relief. For the next three days, the subject will evaluate pain relief generated by the 1st assigned program (arms).

After 3 days, the patient will visit the Ohio Pain Clinic for data collection and then reprogramming of the EPG for the next arm. For the next three days, the subject will evaluate the SCS therapy generated by the 2nd assigned program and then return to the clinic for data collection, removal of the leads and exit from the study. After the subject is exited from the study, he or she will be followed by the Ohio Pain Clinic per usual care. The data collection requirements are listed below.

Enrollment:

- Informed consent signed
- Confirmation of study eligibility

Baseline evaluation:

- Record pain ratings and pain map
- Relevant medical history
- Physical examination
- Brief Pain Inventory
- Demographics

After the lead implantation:

- Implant procedure

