4.0 STUDY DESIGN

The proposed study is a prospective, single-center, two arm, randomized, crossover design to be conducted at The Ohio Pain Clinic. The study will enroll up to 100 subjects in order to assure at least 50 subjects in the study. Subjects selected to participate in the trial have back and/or leg pain, have been identified as a candidate for SCS and have agreed to undergo a temporary SCS trial using the Algovita® system with percutaneous leads. Each subject will be followed during the trial period of approximately 7 days.

The study will end when the last subject has completed the trial period or is exited. The expected enrollment period for this study is approximately three months. After exit from the clinical study, subjects will continue to be followed by their physician per usual care. All device and procedure-related AEs will be collected and reported per the study protocol.

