10.2 ANTICIPATED ADVERSE DEVICE EFFECTS

The following ANTICIPATED EVENTS have been identified as possible complications of implanting neurostimulator leads.

- Infection at implant site
- Pain at implant site
- Bleeding
- Bruising
- Device failure
 - Unintended stimulation
 - Increased stimulation
 - Decreased stimulation
 - Lead breakage/migration
 - Battery depletion
 - Erosion of device
 - General device failure

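### Adverse events are to be compared by an undefined treatment group in a crossover, with no rule tying an event to the pulse width in use when it began

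*Combined protocol and SAP*

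**What the plan says.** The study is a two-period crossover. Patients are randomised to start with a pulse width below 500 or above 1000 μsec, and the Synopsis (Study Procedures) describes the switch: "After 3 days, the patient will visit the Ohio Pain Clinic for data collection and then reprogramming of the EPG for the next arm".

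The safety endpoint in Section 5.2 is a single rate over the whole trial: "Rate of device-related and/or procedure-related AEs from Trial Lead implant through study completion". The Synopsis and Section 2.2 (item 7) use essentially the same window. It covers both programs and pools device- and procedure-related events.

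Section 11.2 sets out the analysis. The safety set is everyone treated. For complications the test is given as follows: "The proportion of patients with complications will be compared by Fisher's Exact test". Two treatment groups are then to be compared by t-test and chi-square test, and adverse events and their "relationship to the treatment procedure will be tabulated and compared by treatment groups". Section 11.2 does not say whether a treatment group is a sequence, a period or a pulse width, and it states no time window.

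Section 10.1 defines an adverse event by attribution to the device or the incision closure procedure, without mention of the program. Section 10.2 lists implant-site infection, pain, bleeding and bruising together with stimulation events such as "Increased stimulation". In Section 9.1.5 the pain rating and the maps are recorded for the current arm. The adverse event item carries no such label.

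**The concern.** The language of Section 11.2 is that of a parallel-group trial. In a crossover the grouping decides what the comparison estimates, and the plan leaves it open. One natural reading contrasts two groups that both received both settings. The other contrasts the settings, but mixes events that could depend on pulse width with events caused by the single lead procedure.

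Section 5.0 says that the endpoints are meant to determine outcomes of the longer against the shorter pulse width, and that safety data are collected throughout. Without an attribution rule, the analyst must choose the grouping after the data are in. A difference in stimulation-related events between settings could then be missed or blurred.

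**Working it through.** The plan gives no adverse event rate, power, alpha or allocation ratio, so there is no figure of its own to reproduce.

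**Inputs.** From the documents: crossover with both programs given (Synopsis; Section 4.0); whole-trial window (Section 5.2); Fisher's test (Section 11.2); at least 50 and at most 100 subjects (Sections 4.0 and 8.3). Assumed for illustration: two-sided 5% level, 1:1 sequences, no dropout, independent periods, no order effects, and an event risk per period of 5% at the shorter setting and 10% to 30% at the longer. The direction is arbitrary and is not a prediction.

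**Reading 1: the groups are the randomised sequences.** Let p_S and p_L be the risks per period. The whole-trial risk in either sequence is

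1 − (1 − p_S)(1 − p_L).

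For 5% and 15%: 1 − 0.95 × 0.85 = 19.25% in both. For 5% and 30%: 1 − 0.95 × 0.70 = 33.5% in both. The formula is symmetric in p_S and p_L, so the expected difference is zero whatever the rates.

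Exact enumeration gives the chance of a significant result for Fisher's test between sequences, and for an exact McNemar test on events assigned to the active program:

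| Risk per period, shorter vs longer | Whole-trial risk, each sequence | Fisher by sequence, N = 50 / 100 | McNemar by program, N = 50 / 100 |
|---|---|---|---|
| 5% vs 10% | 14.5% | 1.8% / 2.3% | 6.9% / 18.7% |
| 5% vs 15% | 19.25% | 2.2% / 2.8% | 25.7% / 58.5% |
| 5% vs 20% | 24.0% | 2.2% / 3.0% | 51.7% / 87.6% |
| 5% vs 30% | 33.5% | 2.5% / 3.0% | 89.7% / 99.8% |

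The sequence comparison rejects at no more than its false-positive rate, however large the pulse-width effect.

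Early exits change this slightly. If a fraction d of each sequence leaves before the switch, expected events per subject are p_S + (1 − d)p_L and p_L + (1 − d)p_S, which differ by d(p_L − p_S). With d = 10% (assumed) and 5% vs 15%, that is 0.10 × 10 = 1 percentage point of a true 10.

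**Reading 2: the groups are the pulse widths, by program at onset.** Suppose a lead-procedure event occurs in period 1 with risk q, whatever the setting. With 1:1 sequences the risk recorded against a setting with risk p is

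½[1 − (1 − q)(1 − p)] + ½p = p + ½q(1 − p).

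For q = 10%:
- shorter: 0.05 + 0.05 × 0.95 = 9.75%
- longer: 0.15 + 0.05 × 0.85 = 19.25%

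The difference falls from 10 to 9.5 points, and the risk ratio from 0.15/0.05 = 3.0 to 0.1925/0.0975 = 1.97. With q = 20% the risks are 14.5% and 23.5%, a ratio of 1.62. This is mainly dilution.

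The allocation ratio is not stated. If a share f starts on the longer setting, ½ becomes f for the longer setting and 1 − f for the shorter. For q = 10% and f = 0.6 the risks are 0.05 + 0.04 × 0.95 = 8.8% and 0.15 + 0.06 × 0.85 = 20.1%, a difference of 11.3 points. For f = 0.4 they are 10.7% and 18.4%, a difference of 7.7. Unequal sequences would therefore turn dilution into bias.

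On this reading each completer contributes to both groups, which Fisher's test treats as separate people.

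**Schedules side by side.** The Synopsis schedule, the Section 4.1 table and the Section 9.1.5 list all place adverse event documentation at follow-up visits. In the Section 9.1.1 table the row for any adverse events is ticked only after implant (the tick positions should be checked in the formatted table).

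**The case against.** The strongest reply is that the data already allow events to be placed. Section 10.1 has the investigator ask about events at each evaluation. Section 9.1.5 lists them at the day 4 and day 7 visits, the first visit comes before reprogramming, and the programmed parameters are documented. Section 9.1.6 also has device- and procedure-related events collected as they occur. A reader might infer that nothing links an event to the active program, and the documents do not support that: an indirect link by visit exists. The draft case report forms are assigned to Appendix 17, which is not in the text reviewed, so an onset-date field can be neither confirmed nor ruled out.

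The protocol also uses arm to mean pulse width, so treatment group in Section 11.2 may mean that too. A reader might conclude that the comparison is uninformative about pulse width on any reading. That is true only of the sequence reading over the whole trial. A reader might also infer that procedure events are systematically charged to the pulse width given first. That applies only to the program reading, and with balanced randomised order it is mainly dilution.

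Finally, the stated endpoint is one overall rate, which remains fully estimable, and no objective claims equal safety of the two settings.

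All of this stands, and it narrows the point without removing it. Section 11.2 does plan a comparison, and no section defines its groups or says to use visit timing. The conflicting schedule also makes visit timing less dependable.

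**Conclusion.** The concern holds in this limited form: the by-group adverse event comparison has no defined group and no attribution rule, and it uses independent-groups tests in a crossover. Read as sequences over the whole trial, its expected difference is zero, ignoring order effects and early exits. That result does not depend on the assumed rates. Read as pulse widths, the contrast is informative but diluted by procedure events, and the pairing is ignored.

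The overall whole-trial rate and the primary endpoint are unaffected. The documents do not show that a safety difference exists or that attribution is impossible. The power figures illustrate what is lost under assumed rates and independent periods. They also show that a within-subject comparison would have modest power for small differences, for example 25.7% for 5% vs 15% with 50 subjects. This should be settled before enrolment, because the active program is best recorded prospectively.

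**What to change.** - Ensure that the adverse event form records the onset date and the pulse-width program active at onset.
- In Section 11.2, define the comparison as device- or stimulation-related events by program active at onset. State how an event continuing across the switch is handled, for example counted once under the program at onset, with later worsening recorded as a new event.
- Use a within-subject method: McNemar's test, or conditional logistic regression with a period term. Give estimates with intervals, and list separately the subjects who received only one program.
- Report lead-procedure events once for all implanted subjects, without assigning them to a pulse width.
- Keep the whole-trial rate as the overall description.
- State the allocation ratio, and reconcile the adverse event rows in the Synopsis schedule, the Section 4.1 table, the Section 9.1.1 table and the Section 9.1.5 list.

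The cost is one or two form fields, a few sentences in Section 11.2 and a little more analysis. No extra visits or patients are needed.
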